#### 5.4.4 Handling of Withdrawals

Every effort will be made to ensure that subjects who withdraw (for whatever reason) from the study continue scheduled evaluations and participate in the follow-up evaluation. Subjects who withdraw due to an AE or SAE will be given appropriate care under medical supervision until the symptoms of any AE resolve or the subject's condition becomes stable.

Subjects who have TNBC and centrally confirmed AR+ status who are enrolled and receive study drug and go on to withdraw will not be replaced. Over-enrollment: Central laboratory confirmation of AR receptor status will not be available at the time of enrollment for most subjects. Subjects will be enrolled into the study based upon their medical history or locally confirmed TNBC AR+ hormonal status. Subjects who are later found after enrollment not to have centrally confirmed AR+ will be replaced by an over-enrolled subject in order for the correct number of eligible AR+ TNBC subjects to be included in the primary analysis. Subjects who are later found not to have centrally confirmed AR+ may, at the discretion of the Investigator, be maintained on the study based on a local finding of AR+, but these subjects will not be part of the evaluable subjects subset of the FAS. Furthermore, subjects who are enrolled but do not receive treatment will also be replaced by an evaluable over-enrolled subject and will not be part of the FAS. This may result in up to an additional 14 subjects being enrolled.

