### 7.3 Treatment Phase

The first dose of study drug will be administered at baseline (Visit 2). GTx-024 will be administered for up to 12 months from the first dose of treatment or until disease progression (whichever is sooner), subject's withdrawal of consent, or intolerability. Subjects who benefit from the treatment at week 16 and still benefit from the treatment at week 24 may continue to receive GTx-024 for a total of 12 months from the date of the first dose of study treatment (as long as they still benefit from the treatment during these 12 months). Subjects who continue to demonstrate a beneficial response at 12 months will be offered to continue in a safety extension study under a separate protocol.

After randomization on Day 1, a safety check involving a comprehensive metabolic panel (Chem 14), including serum calcium and liver function tests, will be performed at Week 2 ( $\pm 3$  days). The Week 2 safety check should include a clinic visit. The investigator may repeat these checks at Week 3 ( $\pm 3$  days) if clinically indicated.

During the first 4 months of the treatment phase, the subjects will be asked to come for a visit every 4 weeks (Visits 3, 4, 5, and 6), and then every 8 weeks (Visit 8 and Visits 10–12 as required if still on treatment). Visits 7 and 9 at weeks 20 and 28 will only take place in subjects who have CR or PR at Visit 6 (week 16) or Visit 8 (week 24), respectively (see below).

The following tests and procedures will be performed during Visits 3, 4, 5, 6, and 8 in the treatment phase:

- Review concomitant medications
- Physical examination, including weight and vital signs (heart rate, respiratory rate, body temperature, blood pressure in a sitting position)
- ECOG performance status
- Blood sampling for: hematology, biochemistry, serum lipid profile, coagulation status, serum hormones, and PSA
- Urine analysis, only if clinically indicated
- Urine pregnancy test for premenopausal subjects (at the site)
- AE collection
- Subjects will be asked to complete a QoL questionnaire
- GTx-024 drug accountability/dispensation

Radiologic assessments for anti-tumor effect will be done every 8 weeks whilst subjects receive treatment (Visit 4, Visit 6, Visit 8, and thereafter). In addition, if a subject has CR or PR at Visit 6 (week 16) or Visit 8 (Week 24), in compliance with RECIST 1.1 guidelines, a confirmation of the CR or PR should be done 4 weeks later (i.e., Visit 7 and/or Visit 9, as

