Protocol: A Phase 2 Open Label, Multi-Center, Multinational Study Investigating The Efficacy and Safety Of GTx-024 On Advanced, Androgen Receptor-Positive Triple Negative Breast Cancer (AR+ TNBC)	Compound No.: GTx-024 Author: [name]
---	---

applicable). The same imaging technique must be used throughout the study in a given subject. Bone scans will be performed at screening and then at weeks 8, 16, and 24 in only those subjects with baseline bone metastases, or if clinically indicated. The central imaging facility will also perform tumor volumetric assessment for the subjects undergoing CT scanning during Visit 6 and Visit 8. Blood sampling for CTC enumeration will be done at the same visits as the radiological assessments during the treatment phase; i.e., every 8 weeks whilst subjects receive treatment (Visits 4, 6, and 8), but not at the confirmation of the CR or PR visits (Visits 7 and 9) or at Visits 10–12.

Dispensing of GTx-024 will be done every 8 weeks: at Visit 4 (week 8), Visit 6 (week 16), Visit 8 (if subject continues treatment after week 24), and thereafter if a subject continues treatment every 8 weeks.

Blood samples for pharmacokinetic assessment will be collected at Visit 3 (week 4), Visit 5 (week 12), Visit 6 (week 16), and Visit 8 (week 24). The exact time (hh:mm) and date of each blood sample will be recorded on the eCRF. The date and approximate time of the last dose of GTx-024 prior to the blood sample should also be recorded; i.e., it should be documented whether the subject took the previous dose that morning or the evening before.

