## 7.6 Early Termination Visit

An early termination visit will happen in case of:

- A subject withdrawing from the study at their decision
- GTx, Inc. terminating the study in the interest of subject welfare
- Investigator withdrawing the subject from the study

Subjects will be asked to attend a final visit so that the procedures for the EOT (see above) may be performed.

Protocol: A Phase 2 Open Label, Multi-Center, Multinational Study Investigating The Efficacy and Safety Of GTx-024 On Advanced, Androgen Receptor-Positive Triple Negative Breast Cancer (AR+ TNBC)	Compound No.: GTx-024 Author: [name]
---	---

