## 8.2.2 Special Assays or Procedures

### Pharmacokinetic assessment:

Blood samples for pharmacokinetic assessment will be collected at baseline (pre-dose), Visit 3 (week 4), Visit 5 (week 12), Visit 6 (week 16), and Visit 8 (week 24). One blood sample will be collected in a 6 mL K2-ethylenediaminetetraacetic acid (EDTA) blood collection tube on each of these days. The exact time (hh:mm) and date that each blood sample is collected will be

Protocol: A Phase 2 Open Label, Multi-Center, Multinational Study Investigating The Efficacy and Safety Of GTx-024 On Advanced, Androgen Receptor-Positive Triple Negative Breast Cancer (AR+ TNBC)	Compound No.: GTx-024 Author: [name]
---	---

recorded on the eCRF. At the baseline visit, the blood sample should be collected before the subject is given their first dose of GTx-024. At visits 3 (week 4), 5 (week 12), 6 (week 16), and 8 (week 24), the date and approximate time of the last dose of GTx-024 prior to the blood sample should be recorded; i.e., it should be documented whether the subject took the previous dose that morning or the evening before. Immediately after collection, the tubes will be gently inverted several times to mix the anticoagulant with the blood sample.

Blood samples will be kept on wet ice (ice packs in a water bath is also acceptable) for up to 20 minutes until processed. The plasma fraction will be separated by placing the collection tube into a centrifuge for 10 minutes at 1,500 x g. The plasma fraction will be withdrawn by pipette and divided into two 2 mL polypropylene transfer vials (with each tube receiving approximately equal aliquots).

All sample collection and freezing tubes will be clearly labeled in a fashion which identifies the subject, the study number, the visit number, and freezing tube aliquot letter. Labels will be fixed to freezing tubes in a manner that will prevent the label from becoming detached after freezing. Samples will be stored in a freezer at  $-20^{\circ}\text{C}$  or lower. Samples will be shipped in a thermal insulated container with sufficient dry ice to assure they remain frozen.

Any remaining plasma samples after completion of the protocol outlined pharmacokinetic analysis may be used to identify and quantify the metabolites of GTx-024.

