#### 11.4.3.4 Tertiary efficacy analysis

The following tertiary efficacy analyses apply to the evaluable subjects and the FAS:

- PSA changes from baseline to each scheduled assessment will be described and tested for a significant change from baseline. Percentage change from baseline will be summarized and analyzed as well.
- QoL: The EQ visual analog scale (VAS) will be summarized by descriptive statistics at baseline and each assessment. Mean changes from baseline will also be summarized using descriptive statistics and 95% confidence intervals. EQ-5D-5L single item scale scores (mobility, self-care, usual activities, pain/discomfort, and anxiety/depression) will be summarized by means of frequency counts at baseline and at each assessment.
- CTCs: changes in the number of CTCs from baseline to each scheduled assessment will be described and tested for a significant change from baseline.
- Duration of prior CB: the impact of duration of prior CB on the current CB response will be explored in an exploratory way using logistic regression models with and without other covariates. The impact of duration of prior CB on PFS, TTP, and duration of response outcomes will be assessed in a Cox proportional hazards model with and without other covariates.
- Time from diagnosis of metastases to enrollment: the impact of time from diagnosis of metastases to study enrollment on the current CB outcome will be explored in an exploratory way using logistic regression models with and without other covariates. The impact of time from diagnosis of metastases to study enrollment on PFS, TTP, and duration of response outcomes will be assessed in a Cox proportional hazards model with and without other covariates.
- Tumor volumetrics: the effect of GTx-024 18 mg on tumor volume will be described visually using waterfall plots.
- GTx-024 and GTx-024 glucuronide plasma concentrations will be assessed for their association with CBR at weeks 16 and 24 using logistic regression by creating binary

Protocol: A Phase 2 Open Label, Multi-Center, Multinational Study Investigating The Efficacy and Safety Of GTx-024 On Advanced, Androgen Receptor-Positive Triple Negative Breast Cancer (AR+ TNBC)	Compound No.: GTx-024 Author: [name]
---	---

variables for the concentrations by dichotomizing at the median concentration at weeks 16 and 24.

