#### 11.4.3.7 Missing data/Outliers/Dropout considerations

No imputation for missing data will be carried out other than to complete partial dates using standard imputation techniques as per the Contract Research Organization's (CRO's) standard.

No evaluable subject will have missing data for the primary efficacy analysis because subjects who have the week 16 assessment will be classified as having CB or not, and those who do not have a week 16 assessment will be classified as not having CB.

With regards to missing start and stop dates for AEs and medications, imputation rules will be provided in the SAP. In addition, rules to determine in which period each AE belongs for the summary tables will also be provided in the SAP.

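### The exposure-response models use concentrations split at the median and do not exclude off-drug samples; continuous concentration limited to on-treatment samples would serve better if the effect is graded

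*Combined protocol and SAP*

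**What the plan says.** The protocol's tertiary objectives (Section 3.1) include the effect of GTx-024 and glucuronide concentrations on the CB rate at weeks 16 and 24. Section 11.4.3.4 sets the method: logistic regression on binary "variables for the concentrations by dichotomizing at the median concentration at weeks 16 and 24".

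Sampling is set in Section 8.2.2: "Blood samples for pharmacokinetic assessment will be collected at baseline (pre-dose), Visit 3 (week 4), Visit 5 (week 12), Visit 6 (week 16"), and again at Visit 8 (week 24). The end-of-treatment visit (Section 7.4) has no pharmacokinetic sample. The date and approximate time of the last dose are recorded, so that "it should be documented whether the subject took the previous dose that morning or the evening before" (Section 7.3). No planned analysis uses that record.

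Dosing has an endpoint: "GTx-024 will be administered for up to 12 months from the first dose of treatment or until disease progression" (Section 7.3). For the primary endpoint, "those who do not have a week 16 assessment will be classified as not having CB" (Section 11.4.3.7). The same section adds: "No imputation for missing data will be carried out other than to complete partial dates".

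Two passages bear on what happens after withdrawal. Section 5.4.4: "Every effort will be made to ensure that subjects who withdraw (for whatever reason) from the study continue scheduled evaluations". Section 7.6: "Subjects will be asked to attend a final visit so that the procedures for the EOT (see above) may be performed".

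Section 11 leaves further detail on tests and missing data to a separate SAP, which is not in the supplied text.

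**The concern.** There are three separate problems.

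1. **The split.** It treats every concentration on the same side of the median as equal. If benefit rises steadily with exposure, that discards information.
2. **Early failures.** A subject who stops before week 16 is a known failure with no scheduled on-treatment concentration at week 16. Outcome known and predictor missing means that failures leave the model selectively. Week 24 should be worse, because by then samples come mainly from subjects kept on treatment.
3. **Off-drug samples.** If a withdrawn subject does return and is sampled, the concentration is low because dosing stopped, and dosing may have stopped because of failure. Nothing in Section 11.4.3.4 keeps that sample out.

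The first two make a null result uninformative. The third works in the opposite direction: stopping the drug after failure would look like low exposure causing failure.

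**Working it through.** **Inputs.** From Sections 11.1 and 11.2: 41 evaluable subjects and a CB rate of 20% under the alternative. Assumed, because the documents give no value: odds ratio (OR) per SD of log concentration of 2 or 3; the share of failures gone by week 16 (30 / 50 / 75%); error-free concentrations; off-drug values below on-drug values.

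**The plan's own figures.** No power is stated for this analysis. The primary design does reproduce. With P(success) = Σ over x from 2 to 21 of Bin(x; 21, p) × P(Bin(20, p) ≥ 5 − x), the type I error is 0.0457 at p = 0.05 and the power 0.9017 at p = 0.20, matching 5% and 90%. Expected events are 41 × 0.20 = 8.2, and expected failures 41 − 8.2 = 32.8.

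**Step 1: the split with complete samples.** Model: logit P(CB) = a + log(OR) × z, with z standard normal and a set to give a 20% rate; likelihood-ratio test at two-sided 5%; simulated.

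| True relation | Continuous | Median split |
|---|---|---|
| Graded, OR 2 / 3 per SD | 0.39 / 0.73 | 0.27 / 0.54 |
| Step at the median, OR 4 | 0.27 | 0.32 |
| Rising below the median (OR 4 per SD), flat above | 0.21 | 0.21 |

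Repeat simulations of the graded case put the split between 0.24 and 0.28 (OR 2) and between 0.45 and 0.54 (OR 3). The loss is therefore clear for a graded effect and absent for a step or plateau.

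**Step 2: early failures leave.** Sampled failures = 32.8 × (1 − share gone); add the 8.2 with CB. Power is for OR 2 / 3, with early failure unrelated to exposure.

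| Share gone | Sampled at week 16 | Split | Week-16 continuous |
|---|---|---|---|
| 30% | 23.0 + 8.2 = 31.2 | 0.27 / 0.51 | 0.39 / 0.68 |
| 50% | 16.4 + 8.2 = 24.6 | 0.24 / 0.46 | 0.36 / 0.65 |
| 75% | 8.2 + 8.2 = 16.4 | 0.20 / 0.37 | 0.29 / 0.51 |

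If low exposure also brings earlier failure, 50% gone gives 0.15 / 0.25 (split) and 0.20 / 0.36 (continuous). At week 24, with 8 to 16 of 41 sampled, the split has 0.06–0.17 / 0.06–0.30 and the continuous model 0.14–0.23 / 0.15–0.41. The failure rule is written for week 16 only; the week-24 figures assume the same rule there.

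**Step 3: off-drug samples, no true effect.** Take 50% of failures gone. On-drug subjects number 24.6, of whom 8.2 / 24.6 = 33% have CB.

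- All 16.4 who left are sampled: 41 in the model, 20.5 on each side. The upper half is all on drug, so CB is 33%. The lower half holds 24.6 − 20.5 = 4.1 on-drug subjects, so CB is 4.1 × 0.33 / 20.5 = 7%.
- A quarter (4.1) are sampled: 28.7 in the model, 14.35 on each side. CB is 33% above. Below, 24.6 − 14.35 = 10.25 are on drug, so CB is 10.25 × 0.33 / 14.35 = 24%.

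Simulated rejection rates of the split at nominal 5%:

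| Share gone | A quarter of them sampled off drug | All of them sampled off drug |
|---|---|---|
| 30% | 0.07 | 0.20 |
| 50% | 0.11 | 0.61 |
| 75% | 0.31 | 0.99 |

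An unrestricted continuous model is worse: at 50% gone it rejects in 0.22 of trials with a quarter sampled and 0.88 with all sampled. On-treatment samples only give 0.06–0.07 at these attrition rates.

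**Step 4: week 4 as an alternative.** If week 4 carries the same exposure signal, continuous week-4 concentration keeps about 0.40 / 0.72 at any of these attrition rates. If instead the week-16 level alone drives CB (30% gone), the result depends on the week-4/week-16 correlation:

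| Correlation | Week-4 continuous | Planned split |
|---|---|---|
| 0.85 | 0.30 / 0.56 | 0.27 / 0.50 |
| 0.7 | 0.23 / 0.42 | 0.27 / 0.50 |
| 0.5 | 0.14 / 0.23 | 0.25 / 0.49 |

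**The case against.** Four points can be made for the plan, and each limits the conclusion.

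**The relation may not be graded.** A reader might infer that the split loses power whatever the truth. Section 2.2 points another way: the fall in SHBG was 18.2% at 10 mg and 18.4% at 30 mg, and the chosen dose range is expected to saturate the receptor. A threshold or plateau is plausible, and then the split loses nothing. This stands, so the power claim is conditional.

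**Off-drug samples should be rare.** A reader might infer that the plan will produce a false association, with rejection rates up to 0.99. That figure needs every early failure to return for a sample. Pharmacokinetic sampling is described under the treatment phase, early terminators are routed to a visit without such a sample, and the last-dose instruction presumes continued dosing. Only the general retention sentence in Section 5.4.4 opens the door. This largely stands. The gap remains, because the analysis section does not close it and partial sampling still matters when attrition is high.

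**The separate SAP may hold the rule.** It may. The absence of an on-treatment restriction is established only for the supplied text. The split itself is fixed in the protocol.

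**Week 4 is not clearly the better exposure.** A reader might conclude that it should become the main model. The documents give no week-4/week-16 correlation, and doses can change later (Sections 6.3 and 9.4). The advantage is gone at a correlation near 0.75 and reverses at 0.5, so week 4 belongs in a supportive role.

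**Conclusion.** The point holds in a conditional form and is worth considering, not critical. For a graded effect of OR 2 / 3 per SD, the split lowers power from 0.39 / 0.73 to 0.27 / 0.54 with complete samples, and continuous concentration stays ahead as failures leave. For a step or plateau there is no loss. Loss of early failures lowers power for any week-16 model, and more so at week 24. Off-drug samples would create a spurious association whose size depends on how many are drawn: slight if few leave and a quarter of them return, large only with high attrition or near-complete return.

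Effect sizes, attrition and off-drug sampling rates are all assumptions. The analysis is tertiary, no decision rule uses it, and with about 8 events any version is exploratory.

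**What to change.** Amend Section 11.4.3.4, or specify in the SAP:

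- Enter concentration as continuous log concentration in place of the median split, for GTx-024 and the glucuronide separately, adjusted for time since last dose.
- Use only samples taken on treatment, meaning study drug neither permanently stopped nor interrupted at sampling. Judge this from the recorded last-dose date and time and the interruption record (Section 6.4). A morning-or-evening rule should not define it: Section 6.2 asks only for roughly the same time each day, so a compliant midday doser would be wrongly excluded.
- Report the number sampled on treatment, the number of samples excluded as off drug, and the number of failures not sampled.
- Add continuous Visit 3 (week 4) concentration as a supportive model that keeps early failures, read alongside the observed week-4/week-16 correlation.
- Keep the median-split result, if wanted, as a descriptive display.

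The first two changes must go together, because a continuous model without the restriction is more exposed to off-drug values than the split is.

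The cost is analysis wording only; the samples and dose times are already collected. The downsides are an assumed log-linear relation, an approximate last-dose time, and power that stays modest.

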#### 11.4.3.5 Safety; AEs/labs/study drug exposure/vitals/other

Routine safety assessments of AEs, laboratory variables (clinical chemistry, hematology, and urinalysis), physical examinations, vital signs, ECOG performance status, and ECGs will be done.

Safety analyses will be conducted among the SAS. AEs will be coded according to the current version of the Medical Dictionary for Regulatory Activities (MedDRA®). AEs, laboratory outcomes, and results from physical examinations will be graded according to NCI-CTCAE, Version 4.0.

Summaries of safety data will be presented for subjects in the FAS with centrally confirmed AR+ status as well as in all subjects enrolled and treated (SAS and FAS).

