## 2.3 Potential Risks and Benefits

### 2.3.1 Potential Risks

GTx-024 has generally been well tolerated in clinical trials conducted to date. Certain AEs associated with GTx-024 may occur. The most commonly reported side effects for GTx-024 in the previous 21 clinical studies include:

- Headache
- Back pain
- Diarrhea
- Pain in arm or leg
- Upset stomach
- Constipation
- Fatigue (tiredness)
- Dizziness
- Increases in liver enzymes
- Flu-like symptoms
- Anemia (decrease in red blood cells)
- Reduction in high density lipoproteins
- Visual disturbances

These side effects were based on information obtained from clinical studies using GTx-024 in doses ranging from 0.1 mg to 3 mg. These studies suggest that side effects associated with the study drug resolve after GTx-024 is stopped.

In a Phase 2 clinical study using GTx-024 in cancer subjects, the following serious adverse events (SAEs) occurred in at least 2% but less than 10% of subjects. These SAEs are also consistent with the subject's cancer therapy and the severity of the illness, and, therefore, may have resulted from the GTx-024 or from the cancer progression and/or the cancer treatment:

- Febrile neutropenia
- Pneumonia
- In an ongoing phase 2 study of GTx-024 in ER+/AR+ breast cancer, clinically significant hypercalcemia has been observed that was assessed by the investigators as possibly related to an 18 mg dose of GTx-024.

An AE that appears related to GTx-024 in clinical trials has been a dose-dependent, transient, asymptomatic increase in ALT. However, these increases were modest at doses up to 10 mg per day. Most of the subjects studied to date had ALT levels that remained within normal limits. One subject was discontinued for an ALT > 3 times the ULN. The ALT levels returned to normal with continued exposure to GTx-024 in most cases and, further, in instances when dosing was not continued, levels returned to normal. No significant increases in total bilirubin, gamma glutamyl transferase, alkaline phosphatase, or lactate dehydrogenase (LDH) have been

Protocol: A Phase 2 Open Label, Multi-Center, Multinational Study Investigating The Efficacy and Safety Of GTx-024 On Advanced, Androgen Receptor-Positive Triple Negative Breast Cancer (AR+ TNBC)	Compound No.: GTx-024 Author: [name]
---	---

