**Safety objective:**

To describe the safety profile of GTx-024 18 mg PO daily in subjects with TNBC and centrally confirmed AR+ as well as in all subjects enrolled and treated.

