### 6.3 Modification of Study Investigational Product Dosing for a Subject

With the exception of elevated LFTs and hypercalcemia, both of which are further addressed below, subjects who experience an AE with Grade  $\geq 3$  intensity (NCI-CTCAE, Version 4.0) and/or intolerance may have a dose reduction from 18 mg to 9 mg per day or a drug interruption based on the medical judgment of the Investigator and after confirmation by the study Medical Monitor. The drug interruption may last for a period of up to 7 days after which the subject must be rechallenged with study drug (18 mg or 9 mg) or discontinued from the study. In the case of a dose reduction, once the AE has resolved or reduced in intensity to Grade 1, the subject may be rechallenged with 18 mg or maintained at 9 mg at the discretion of the Investigator.

For  $\geq$  Grade 3 elevations in LFTs, study drug should be held. A recheck of LFTs should be done within 48 hours. At the discretion of the investigator, study drug may be restarted at the 18mg dose or reduced to a 9mg dose when the LFTs have resolved to Grade 1 or better.

In the event of hepatotoxicity, please also refer to [Section 9.4](#) [Halting Rules](#).

In the event of  $\geq$  Grade 2 hypercalcemia, study drug should be held until hypercalcemia resolves to Grade 1 or better.

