## 9.4 Halting Rules

If in the opinion of the Investigator, the participation in the study is or is becoming detrimental to the well-being of a particular subject, this issue should be discussed with the Medical Monitor for this study and a determination made regarding dose reduction, interruption, or withdrawal of the subject from the study.

Withdrawal of the subject from the study should be considered if:

- ALT or AST  $> 8 \times$  ULN
- ALT or AST  $> 5 \times$  ULN for more than 2 weeks
- ALT or AST  $> 3 \times$  ULN and (total bilirubin  $> 2 \times$  ULN or INR  $> 1.5$ )
- ALT or AST  $> 3 \times$  ULN with the appearance of fatigue, nausea, vomiting, right upper quadrant pain or tenderness, fever, rash, and/or eosinophilia ( $> 5\%$ )

For subjects with known liver metastasis and elevated ALT or AST of  $\leq 5 \times$  ULN at baseline, discontinuation of treatment should be considered if:

- ALT or AST  $> 5 \times$  ULN and total bilirubin  $> 2 \times$  ULN

All subjects discontinued from the study should be followed until abnormal values return to normal.

ALL DISCONTINUATIONS SHOULD BE DISCUSSED WITH THE MEDICAL MONITOR PRIOR TO DISCONTINUATION.

If any 2 out of the first 10 subjects enrolled in the study meet the above hepatotoxicity criteria, or if a total of 5 subjects ever meet these criteria and hepatotoxicity is not attributable to an underlying condition (i.e. liver progression), then the 18 mg dose will be reduced to 9 mg for all subjects; i.e., all subjects that are receiving 18 mg will be reduced to 9 mg and all newly enrolled subjects will receive a 9 mg dose. If any of these criteria are met in a total of 5 subjects following the study wide reduction to the 9 mg dose, the study will be halted (i.e., there will be no dose reduction, only study drug discontinuation).

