### 11.4 Final Analysis Plan

#### 11.4.1 Analysis sets

Full Analysis Set (FAS): All subjects who are enrolled and receive at least one dose of study drug.

Evaluable subjects: Subjects in the FAS who have centrally confirmed AR+ status; these subjects are the subjects in the primary efficacy analysis.

Per Protocol Set (PPS): All subjects with centrally confirmed AR+ who have baseline scans and complete the week 16 RECIST 1.1 evaluation, receive at least 80% of the anticipated 18 mg dose, and have no major protocol deviations.

Safety Analysis Set (SAS): All subjects who are enrolled and receive at least one dose of study drug.

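### If the study-wide reduction to 9 mg is triggered, safety tables that pool all treated subjects would understate the 18 mg incidence of dose-dependent liver events

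*Combined protocol and SAP*

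**What the plan says.** The safety objective in Section 3.1 is tied to one dose: "To describe the safety profile of GTx-024 18 mg PO daily in subjects with TNBC and centrally confirmed AR"+, and also in all subjects enrolled and treated.

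Section 11.4.1 defines the analysis population without reference to dose: "Safety Analysis Set (SAS): All subjects who are enrolled and receive at least one dose of study drug". Section 11.4.3.5 then plans the analysis: "Safety analyses will be conducted among the SAS". It names two groups for the summaries, the centrally confirmed AR+ subjects and everyone treated: "as well as in all subjects enrolled and treated (SAS and FAS"). Its heading mentions study drug exposure, but its text plans no exposure summary and no split by dose.

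There are two routes to 9 mg:

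- **Individual.** Under Section 6.3 a subject with a Grade 3 or higher event or intolerance "may have a dose reduction from 18 mg to 9 mg per day or a drug interruption", and may later return to 18 mg. After a hold for raised liver tests she may restart at either dose.
- **Study-wide.** Under Section 9.4, if 2 of the first 10 subjects or 5 in total meet the hepatotoxicity criteria, everyone on 18 mg moves to 9 mg and "all newly enrolled subjects will receive a 9 mg dose".

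Section 2.3.1 describes the ALT rise as dose-dependent and adds: "However, these increases were modest at doses up to 10 mg per day".

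**The concern.** The label on the estimate and the population behind it can come apart. After a study-wide switch, new subjects never take 18 mg but still join the SAS. On the protocol's own account of the ALT effect, they would be expected to have fewer liver events. A pooled incidence read as the 18 mg profile would then be too low.

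The switch is also not independent of the quantity being estimated. It is triggered by liver events, so it is most likely when liver toxicity at 18 mg is common, which is when an accurate 18 mg rate matters most. Section 2.2 describes longer dosing at 1, 3 and 9 mg and 14-day dosing at 10 and 30 mg, so safety under sustained 18 mg dosing is an important part of what this trial would add.

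**Working it through.** **The plan's own figures.** The documents give no safety rate, precision target or by-dose figure to reproduce. The only design calculation is the Simon efficacy design. It reproduces (21 then 41 subjects, at least 2 then at least 5 with clinical benefit; exact one-sided alpha 0.0457, power 0.9017), but it has no bearing on this point.

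**Inputs from the protocol.** Maximum enrolment is 55 (Section 11.2). The triggers are 2 of the first 10 subjects, or 5 in total (Section 9.4).

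**Assumed inputs.** The per-subject risk of a qualifying liver event is q18 for an 18 mg start and q9 for a 9 mg start.

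**Step 1: how likely is the switch?** Suppose each subject at 18 mg independently has risk q18. The chance that either trigger is met within 55 subjects is

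1 − Σ(x = 0, 1) P[Bin(10, q18) = x] × P[Bin(45, q18) ≤ 4 − x].

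| Assumed q18 | 2 of first 10 | Either trigger within 55 |
|---|---|---|
| 2% | 0.016 | 0.02 |
| 5% | 0.086 | 0.19 |
| 10% | 0.264 | 0.69 |
| 20% | 0.624 | 0.99 |

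**Step 2: what would the pooled table show?** If n18 of the 55 start at 18 mg and the rest at 9 mg, the expected pooled incidence is [n18 × q18 + (55 − n18) × q9] / 55. For example, with n18 = 10, q18 = 20% and q9 = 5%: (2 + 2.25)/55 = 7.7%. With q18 = 20% throughout:

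| Started at 18 mg | q9 = 0 | q9 = 2% | q9 = 5% | q9 = 10% |
|---|---|---|---|---|
| 10 of 55 | 3.6% | 5.3% | 7.7% | 11.8% |
| 20 of 55 | 7.3% | 8.5% | 10.5% | 13.6% |
| 30 of 55 | 10.9% | 11.8% | 13.2% | 15.5% |
| 40 of 55 | 14.5% | 15.1% | 15.9% | 17.3% |
| 55 of 55 | 20% | 20% | 20% | 20% |

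If q9 = q18, there is no dilution in any row.

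**Step 3: two illustrative observed results, with no events at 9 mg** (exact 95% CIs).

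- Switch after 2 cases in 10 subjects: 2/10 = 20.0% (2.5-55.6%) by starting dose, against 2/55 = 3.6% (0.4-12.5%) pooled.
- Switch at the fifth case, after 30 subjects: 5/30 = 16.7% (5.6-34.7%) by starting dose, against 5/55 = 9.1% (3.0-20.0%) pooled.

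**Step 4: what do individual reductions do?** A subject reduced after her own liver event started at 18 mg and is already counted as a case, so numerator and denominator are unchanged. Individual reductions mainly shorten time at risk on 18 mg and blur which dose a later event belongs to.

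**The case against.** **Deferral.** Section 11 calls itself an overview. It leaves table specifications, and the rules assigning each AE to a period, to a separate SAP, so a by-dose table is not excluded. That is true. But the deferred rule in Section 11.4.3.7 concerns period and does not mention dose, and nothing in the combined document commits to a by-dose summary. The grouping that Section 11.4.3.5 does state would give the wrong 18 mg rate after a switch.

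**Pooling can be legitimate.** For subjects who start at 18 mg, incidence under the 18 mg regimen with its permitted reductions is a reasonable descriptive target. This stands, and it is why a split by starting dose is the main remedy.

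**A stronger reading.** A reader might infer that 18 mg liver toxicity is diluted whenever anyone receives 9 mg, or that the understatement is 2.6- to 5.5-fold. The documents support neither. Step 4 answers the first. The second compares 20% with a pooled 7.7% or 3.6%, which requires exactly 10 subjects to start at 18 mg and accrual then to reach 55. Section 9.4 states no pause after the tenth subject and no time limit on counting, so more subjects could have started 18 mg before a second case appears. The 20% is also conditional on the trigger: given at least 2 cases in 10, the mean observed rate is about 21%, 23% or 28% when the true risk is 5%, 10% or 20%. At a true 5%, a pooled 3.6-7.7% is nearer the truth than 20%.

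**Other safeguards.** The objective is descriptive, severe liver cases are reported as SAEs, abnormal laboratory values are listed, and a study-wide switch would be conspicuous. These limit the harm but do not correct the incidence in the summary tables.

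**Conclusion.** The concern holds conditionally. If the Section 9.4 switch occurs and liver risk is lower at 9 mg, the planned tables understate the 18 mg incidence; otherwise the dilution of per-subject incidence is small or nil.

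The size depends on when the switch occurs and on rates the documents do not give. With 20% assumed at 18 mg and 2-10% at 9 mg, dilution is modest after a late switch (about 15-17% pooled with 40 of 55 started at 18 mg) and large after a very early one (about 5-12% with 10 of 55, or 3.6% if the 9 mg rate is zero). The 2/10 case is the extreme end and is imprecise. Reading the plan as unable to meet its safety objective would go too far: without a switch, the pooled table describes subjects who all started at 18 mg. The point concerns the safety summaries only; the efficacy test is not in question and no view is taken on any dose rule.

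**What to change.** In Section 11.4.3.5 or the SAP:

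- Present treatment-emergent AE and laboratory summaries by starting dose (18 mg, 9 mg) alongside the pooled SAS table, and base the 18 mg profile on subjects who started at 18 mg. Restricting to treatment-emergent events matters because Section 9.1.1 collects AEs from consent.
- As a supplement, tabulate treatment-emergent AEs and laboratory values by dose at onset or sampling, with exposure time at each dose. State two cautions: in reduced subjects the dose is confounded with time on treatment, and an event may appear only after a reduction.
- Confirm that the eCRF records dose-change dates. Section 9.1.1 collects AE onset, but Section 6.4 names only interruptions and discontinuations for the accountability form.

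The cost is some SAP wording and extra table columns, plus possibly one eCRF field. The downside is smaller counts per column and a possibly less favourable 18 mg rate. No dose rule, sample size or efficacy analysis changes.
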